#### 5 SAFETY AND ADVERSE EVENTS

#### 5. 1 Definition of Adverse Event

Unanticipated Problems Involving Risk to Subjects or Others (UPIRTSO) - any unanticipated problem or adverse event that meets the following three criteria:

Serious: Serious problems or events that results in significant harm, (which may be physical, psychological, financial, social, economic, or legal) or increased risk for the subject or others (including individuals who are not research subjects). These include: (1) death; (2) life threatening adverse experience; (3) hospitalization - inpatient, new, or prolonged; (4)

disability/incapacity - persistent or significant; (5) breach of confidentiality and (6) other problems, events, or new information (i.e. publications, interim findings, product labeling change) that in the opinion of the local investigator may adversely affect the rights, safety, or welfare of the subjects or others, or substantially compromise the research data, AND

Unanticipated: (i.e. unexpected) problems or events are those that are not already described as potential risks in the protocol, consent document, not listed in the Investigator's Brochure, or not part of an underlying disease. A problem or event is "unanticipated" when it was unforeseeable at the time of its occurrence. A problem or event is "unanticipated" when it occurs at an increased frequency or at an increased severity than expected, AND

Related: A problem or event is "related" if it is possibly related to the research procedures.

Adverse Event - an untoward or undesirable experience associated with the use of a medical product (i.e. drug, device, biologic) in a patient or research subject.

Serious Adverse Event - adverse events are classified as serious or non-serious. Serious problems/events can be well defined and include:

- Death
- Life threatening adverse experience
- Hospitalization
- Inpatient, new, or prolonged; disability/incapacity
- And/or per protocol may be problems/events that in the opinion of the sponsor-investigator may have adversely affected the rights, safety, or welfare of the subjects or others, or substantially compromised the research data.

All AEs that do not meet any of the criteria for serious, should be regarded as non-serious AEs.

## 5.2 Adverse Event Reporting Period

For the current study, the treatment follow-up period is defined as 3 months following the last administration of study treatment or 9 months from the initiation of the study, whichever is greater.

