## 4.2 Study Schema

Once patients have agreed to receive further information on the study, an initial consult will be established. Patients who are currently taking other therapies for PD will be requested to stop these therapies for a minimum of 4 weeks prior to the appointment to assure an adequate washout period prior to being enrolled.

During the initial appointment, the patient will receive a description of the study, initial education on how to use the device properly, and informed consent. Those consenting to the procedure will

receive initial study assessments (see below). Those wishing additional time to consider enrollment may be rescheduled to a later date if desired. Once consent is completed, the patients will be randomized into one of four groups: PTT 30 min 1x/day, 30 min 2x/day, 30 min 3x/day, or control (no treatment).

Patients will then begin using the devices as previously instructed for the times appropriate to their group. After 3 months (+1.5 months permitted), patients will return for subsequent assessments (see below). After completion of the subsequent assessments, patients will begin a 3-month, open-label phase of the trial. During this period, the patients will be allowed to use the device for 30 minutes at a time, with a frequency to be determined by the patient.

After completion of the open-phase portion of the trial, patients will undergo final assessments, which are identical to the 3-month assessments. Patients will then be encouraged to self-report any additional adverse events (AE's) that they encounter over the subsequent 3 months after discontinuing the therapy and will be contacted by telephone for a final question / adverse event assessment (9 months after study initiation).

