#### 4.2.2 Subsequent Study Assessments

- Obtained at 3 and 6-month time points
- Objective assessments individual obtaining assessments will be blinded to study arm
  - o Penile length measured from pubic symphysis to glanular corona and penile tip
  - o Penile curvature
    - Measured in A/P and lateral planes using a goniometer (per standard protocol)
    - Direction of curvature also assessed

- O Distance to curve measured from concave portion of curvature to corona of glans
- o Indentations / hourglass deformities noted
- Photographs (if previously obtained and where possible) will be taken at the 3 and 6 month visits
- Subjective questionnaires (attached)
  - o IIEF-15
  - o PDQ
  - Additional questions (3 and 6-month form)

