## 5.6 Recording of Adverse Events

The study team will seek information on adverse events by specific questioning between baseline and the 3 month and 6 month visits. At 9 months from the date of study initiation, the patient will be contacted via telephone for an additional assessment of any adverse events experienced. Information on all adverse events will be recorded immediately in the adverse event section of the specific questionnaire as well as in an adverse event form (see **Attachment – Adverse Event Form**).

All adverse events occurring during the study period will be recorded. The clinical course will be followed until resolution, stabilization, or until it has been ultimately determined that the study treatment or participation is not the probable cause. Serious adverse events that are still ongoing at the end of the study period will be followed up, to determine the final outcome. Any serious adverse event that occurs after the study period and is considered to be at least possibly related to the study treatment or study participation will be recorded and reported immediately.

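### For a man whose 3-month visit is late and who uses the device to the end of open label, the month-9 adverse event call comes up to 1.5 months before his follow-up period ends

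*Combined protocol and SAP*

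**What the plan says.** Section 5.2 (Adverse Event Reporting Period) sets the length of follow-up as "3 months following the last administration of study treatment or 9 months from the initiation of the study, whichever is greater".

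Section 4.2 (Study Schema) sets the calendar. "After 3 months (+1.5 months permitted), patients will return for subsequent assessments". Once those assessments are done, "patients will begin a 3-month, open-label phase of the trial". Then, "After completion of the open-phase portion of the trial, patients will undergo final assessments". After that, men are encouraged to report on their own any events "that they encounter over the subsequent 3 months after discontinuing the therapy". The same sentence adds a closing telephone assessment, placed 9 months after initiation. Section 4.2.2 describes the follow-up assessments as "Obtained at 3 and 6-month time points"; neither section gives a window for the 6-month visit.

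Section 5.6 (Recording of Adverse Events) has the team ask specifically about events at the 3- and 6-month visits. It then repeats the date of the call: "At 9 months from the date of study initiation, the patient will be contacted via telephone for an additional assessment".

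Section 5.4 (Post-study Adverse Event) provides for follow-up of unresolved events. It also provides a telephone review, within 3 months of study completion, of events that the man or his physician thinks may be related to participation. It gives no date for this review.

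On a separate matter, section 5.7.1 says that the form for any serious adverse event (SAE) is reported to the IRB. It ends by limiting IRB reports to directly related SAEs/UPIRTSOs.

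**The concern.** The follow-up period moves with the man's last use of the device, but the only dated, solicited contact after treatment does not. If his 3-month visit slips, everything after it slips too, and the call can fall before the period it is meant to close.

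Safety is the primary objective, and section 2.1 expressly includes open-label use. Section 4.3.3 judges AE differences partly on the total number of events reported. That count depends on how long events are asked about. With the call fixed at month 9, men would be asked about different lengths of time off the device according to how punctual one visit was.

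**Working it through.** **Inputs**
- Delay of the 3-month visit, d: 0 to 1.5 months (section 4.2).
- Open-label phase: 3 months, starting after that visit (section 4.2).
- End of follow-up: the later of last use + 3 months and month 9 (section 5.2).
- Final call: month 9 (sections 4.2 and 5.6).
- Assumption 1: initiation means each man's own start.
- Assumption 2: he uses the device to the end of open label.

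**Formulas**
- Last use: L = (3 + d) + 3 = 6 + d
- End of period: E = max(L + 3, 9)
- Gap between call and end of period: E − 9 = max(0, L − 6)

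**The plan's own figure.** With d = 0, L = 6 and E = 3 + 3 + 3 = 9. This matches the stated month 9, so the schedule is consistent for a man who is on time.

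**Late 3-month visit, use to the end of open label**

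| d (months) | Last use L | Period ends E | Call after last use, 9 − L | Gap E − 9 | Gap / 3 |
|---|---|---|---|---|---|
| 0 | 6.0 | 9.0 | 3.0 | 0 | 0% |
| 0.5 | 6.5 | 9.5 | 2.5 | 0.5 | 17% |
| 1.0 | 7.0 | 10.0 | 2.0 | 1.0 | 33% |
| 1.5 | 7.5 | 10.5 | 1.5 | 1.5 | 50% |

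**Full delay (d = 1.5) but earlier stop.** Last use at month 6 or before gives E = 9 and no gap. Last use at month 6.5 gives a gap of 0.5, and at month 7 a gap of 1.0. A late visit alone is therefore not enough; use must continue past month 6.

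**Could the 6-month visit stay at calendar month 6?** For a man first seen at month 4.5, open label would then last 6 − 4.5 = 1.5 months. The gap would vanish, but the phase would be half the 3 months that section 4.2 states.

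**What the later-of clause does.** It extends the period past month 9 only when L is greater than 6. Those are exactly the men for whom the fixed call is early.

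**IRB sentences (no arithmetic).** An SAE judged not directly related is reportable under the opening sentences of section 5.7.1 and not under its last sentence. The section also leaves the sponsor-investigator to decide which reports are needed and refers to an IRB policy that the documents do not contain. Neither settles which rule applies.

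**The case against.** The strongest reply is that a reporting period is not a contact schedule. Section 5.2 does not require a solicited contact on its last day, and both provisions can be followed as written. Self-report runs for 3 months after stopping, so it moves with the delay. The 9 months may also be nominal, 3 + 3 + 3, just as the visits keep their 3- and 6-month labels when they slip. The section 5.4 review is tied to study completion, so it could reach month 10.5 for a man at the full window.

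Much of this stands. It shows that the plan does not abandon these men and that the authors may have meant a moving date. It does not remove the point. Section 5.6 counts the 9 months from the date of initiation. The section 5.4 review has no date, does not define completion, and covers only events thought to be related, whereas section 5.6 calls for all events in the study period to be recorded. Self-report is only encouraged.

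It is also fair that the practical effect may be small. Time on the device is covered by specific questioning at visits, unresolved events are followed, and section 5.6 still records later SAEs that are at least possibly related.

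Three stronger readings are tempting, and the documents support none of them:
- A reader might infer a gap longer than 1.5 months because the 6-month visit has no window. That needs an assumed further delay with use continuing beyond the stated 3-month phase.
- A reader might infer that the arms are compared unfairly. A late visit can happen in any arm, so the text alone shows no bias between arms.
- A reader might take the IRB wording as adding weight to the timing point. It is a different matter: AE forms are completed either way, so no safety data are lost through it.

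**Conclusion.** The concern holds in a limited, conditional form. For a man whose 3-month visit is d months late and who uses the device to the end of open label, the month-9 call falls d months before his section 5.2 period ends. Under the stated window the gap is at most 1.5 months. It is zero for men who were on time or who stopped by month 6.

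This rests on reading initiation as each man's own start and the 9 months as literal. The documents do not settle the second reading. They also give no distribution of delays, so the share of men affected is unknown. The randomised phase is unaffected. What is lost is dated, solicited collection of new-onset events late in the post-use period, not all AE collection.

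The change is worth making because safety is the primary objective and the remedy is cheap. The two IRB rules in section 5.7.1 are a real but minor inconsistency, to be handled on its own.

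**What to change.** Reconcile sections 4.2, 5.2, 5.4 and 5.6. Time the final AE call from each man's own dates, at the end of his section 5.2 period, and define study initiation and study completion per patient. A call tied to last use would also stay aligned if the 6-month visit slipped.

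The cost is a wording change. Some calls move later by the length of the man's own delay, up to 1.5 months under the stated window. No call or visit is added.

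Separately, reconcile the sentences in section 5.7.1 so that one IRB-reporting rule applies. This review does not say which threshold is right; any change in the number of IRB reports depends on the rule settled on.

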## **5.3** Preexisting Condition

A preexisting condition is one that is present at the start of the study. A preexisting condition should be recorded as an adverse event if the frequency, intensity, or the character of the condition worsens during the study period.

At screening, any clinically significant abnormality should be recorded as a preexisting condition. At the end of the study, any new clinically significant findings/abnormalities that meet the definition of an adverse event must also be recorded and documented as an adverse event.

## 5.4 Post-study Adverse Event

All unresolved AEs will be followed by the study team until the events are resolved, the subject is lost to follow-up, or the AE is otherwise explained. A review of AEs which the subject or subject's physician believe might reasonably be related to participation in the study will be performed at the 6 month follow-up as well as via telephone up to 3 months following study completion.

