#### 2 SPECIFIC AIMS / HYPOTHESIS

## 2.1 Primary Objectives

1. Evaluate the safety of the RestoreX® device when used 30 minutes once daily, twice daily, three times daily, and in an open label fashion

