#### 4.3.3 Statistical Analysis

All data will be entered into JMP Pro 10.0.0 (SAS Institute, Cary, NC). Differences between groupings will be analyzed using tests appropriate to the specific conditions: Wilcoxon, matchedpairs, student's t-test, ANOVA, ANCOVA, chi-squared, or Fisher's tests. All relevant tests will be 2-sided, with a p-value of <0.05 defined as significant. Differences in AE's will be determined based on total number of reported events as well as individual assessments of each individual event.

During the first phase of the study, results will be analyzed as a whole to determine the percentage of men who were non-compliant (both in methods of utilizing the device and percentage of time spent using the device) or dropped out. These data will determine the ability of men to utilize the device as recommended. Data will be analyzed both with and without these non-compliant / dropout men included. Non-compliance will be determined by failure to bury the white indicator line regularly with straight stretch, failure to achieve 90 degree bending during majority of uses, and failure to perform traction for at least 90% of days recommended.

Analyses will be performed using comparisons within patients (changes from baseline to 3 months, from 3 months to 6 months, from baseline to 6 months) and between groupings. ANCOVA will be used (adjusting for baseline values of curvature direction, curvature degree, and baseline penile length). Additional analyses will be performed to analyze the impact of prior treatments (such as intralesional injections) on outcomes. The use of ANCOVA is anticipated to increase the effect size slightly to 0.302 (assuming R^2 value of 0.2 for curvature direction, curvature degree, and baseline penile length).

Assessments will also be performed comparing any degree of traction (i.e. groups 2-4) against no traction. Additional assessment will also be performed based on the total duration of traction applied (time per day multiplied by number of days used) to assess for differences in outcome variables.

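### The AE definition in 5.1 is tied to product use and fits the untreated control arm poorly; 5.4 and 5.6 also describe the 6-month and telephone AE review differently

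*Combined protocol and SAP*

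**What the plan says.** The only primary objective (section 2.1) is to "Evaluate the safety of the RestoreX® device when used 30 minutes once daily, twice daily, three times daily, and in an open label fashion". Section 4.3.3 states the analysis: "Differences in AE's will be determined based on total number of reported events", together with an assessment of each individual event. It also plans to compare any traction with no traction. Section 4.2 randomises men to three traction schedules or to a control group with no treatment for about 3 months, after which patients enter a 3-month open-label phase.

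Three parts of section 5 decide what is counted:

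- **5.1 (definition).** An AE is "an untoward or undesirable experience associated with the use of a medical product (i.e. drug, device, biologic) in a patient or research subject".
- **5.6 (recording).** The team asks specifically about AEs through the 3-month and 6-month visits and asks about any AE at the 9-month call. "All adverse events occurring during the study period will be recorded".
- **5.4 (post-study).** After a sentence on following unresolved events, it says that a review of the events the subject or his physician "believe might reasonably be related to participation in the study will be performed at the 6 month follow-up". The contacts it names are that 6-month visit and a later telephone call.

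Section 5.7.1 lists relationship to study as a separate field on the AE form. Section 4.3.3 does not say whether that field selects the events to be analysed.

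**The concern.** When safety is the primary objective and groups are compared on event totals, the rule for what counts as an event defines the outcome. It should work the same way in every arm and should not depend on who thinks what caused the event.

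There are two separate weaknesses.

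1. **Definition.** A definition that needs a link to product use fits men who have a device. It is unclear for control men, who have none in months 0-3. If their background symptoms are not recorded as AEs, the comparison loses the background rate that a control arm is there to supply, and the error runs towards an apparent device excess.
2. **Belief.** Patients know their assignment and their own device use. If the 6-month visit and the call pick up only events that someone suspects are related, the count depends on expectation, and the error runs towards too few events in the open-label phase. Open-label safety is itself part of the primary objective.

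**Working it through.** **The plan's own figures.** The plan states no AE rate, detectable AE difference or AE power. Its one power calculation is for curvature: f = 0.3370 with 25 in each of 4 arms, 80% power and 5% significance. The noncentral F distribution (3 and 96 df, noncentrality 100 × f²) gives f = 0.33699, so it reproduces. Nothing below depends on it.

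**Step 1. Which rule applies to which contact.**

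| Contact | 5.4 | 5.6 | 5.1 definition matters because |
|---|---|---|---|
| 3-month visit (end of randomised phase) | not mentioned | AEs, no belief filter | controls have had no device |
| 6-month visit (end of open-label phase) | events believed related | AEs, no belief filter | all men have entered the open-label phase |
| Telephone call at 9 months | events believed related | any AE | as above |

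The belief wording therefore cannot affect the randomised 3-month comparison. Only the definition can. Section 5.6 does not cure that, because its all-events sentence covers only what 5.1 calls an AE. Section 5.3 likewise refers new end-of-study findings back to the AE definition.

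**Step 2. How much the definition could matter.** Inputs from the plan: 25 men per arm, so 75 traction v 25 control; two-sided tests at 0.05. Assumptions: the same background risk in every man, no device effect, at most one event per man, and every control event excluded. The last is a deliberate extreme.

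- At 20% risk, expected counts are 0.20 × 75 = 15 and 0.20 × 25 = 5.
- One rule for all arms: 15/75 v 5/25, Fisher p = 1.0.
- Control events excluded: 15/75 v 0/25, p = 0.019.
- A single traction arm v control: 5/25 v 0/25, p = 0.0502, just short of significance.

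The chance of a false p < 0.05 in the pooled comparison is the sum of the binomial probabilities of all outcomes with Fisher p < 0.05. With no control events counted, this needs at least 12 events among the 75 (12/75 v 0/25, p = 0.034; 11/75 gives p = 0.061).

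| Assumed background risk | Control events all excluded | One rule for all arms |
|---|---|---|
| 5% | about 0% | 2.2% |
| 10% | 7% | 2.7% |
| 20% | 84% | 3.4% |
| 30% | 99.8% | 3.8% |

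**Step 3. How much the belief filter could matter.** Suppose a share u of the events raised at the 6-month visit and the call is believed unrelated. If 5.4 were applied as a filter, the 5.6 count would be 1/(1 − u) times the 5.4 count: 1.11 for u = 10%, 1.33 for 25%, 2.0 for 50% and 4.0 for 75%. The plan gives no value of u.

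**The case against.** The case on the other side is substantial.

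- **5.4 is not a recording rule.** It describes a review, never says that other events are left out, and sits under a post-study heading. Section 5.6 is headed as the recording section and is explicit. Staff could follow both. This stands. A reader might infer that only believed-related events are collected from 6 months on, but the documents do not support that.
- **The definition can be read generously.** Association may be temporal; the definition is not limited to the study device; controls also undergo pharmacologic erection for curvature assessment; and 5.3 records worsening of preexisting conditions with no device condition. No passage tells staff to drop control events. This stands against any claim that control events will be zero. It does not settle how a new background symptom in an untreated man is classified, which no passage addresses.
- **The primary objective names device schedules, not control.** True, and for those arms the definition does not differ. But 4.3.3 compares event totals between groupings and plans a traction v no-traction assessment, so the control count is still needed.
- **The AE form and questionnaire are attachments outside the text available.** Their questions may already be the same for all arms. That cannot be confirmed or excluded here.
- **Relationship is already a separate form field.** This stands. It suggests that events are recorded before cause is judged, and it makes the fix easy.

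**Conclusion.** The point holds in a limited form. The definition in 5.1, carried into 5.6, does not clearly cover background events in untreated controls during months 0-3. A literal reading would under-count them and bias the comparison of AEs between traction and control. The size is unknown. The 15/75 v 0/25 result and the false-positive chances of about 0% to 99.8% rest on assumed risks and on every control event being excluded. They show what a strict reading could do and are not a forecast. It would be wrong to conclude from them that the trial will report a false 20-point excess.

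The difference between 5.4 and 5.6 is real but lesser. It concerns the 6-month visit and the call only, 5.6 is the more explicit rule, and 5.4 can be read as an additional review. It should be reconciled; it is not evidence that events will be missed. The two effects would also run in opposite directions, so no net bias across the whole study can be stated.

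The change is worth making because these are the counts for the primary objective in a trial where patients know their assignment. Confidence is medium, given the generous readings available and the unseen forms.

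**What to change.** 1. **Section 5.1:** define an AE as any untoward event in a participant in any arm, whether or not a device is used and whatever the suspected cause.
2. **Section 5.4:** remove the belief condition so that it agrees with 5.6, and state that the same questions are asked in all arms at 3 months, 6 months and the telephone call. Check the attached questionnaire and AE form against this wording.
3. **Section 4.3.3:** state that the AE comparison uses all recorded events, and that related events, taken from the existing relationship field, are reported as a subset.

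The rule in 5.7.1 on what goes to the IRB concerns reporting, not collection, and need not change for this purpose.

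The cost is a few sentences and a few more minor events recorded. No visit, form field or sample size changes.
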